This device qualifies as a non-significant device for several reasons in accordance with 812.2: A) It is not a significant risk device. Study participants will only have contact with a chin and forehead rest and eye movements recorded with a camera in response to a stimulus on a screen about 1 meter away. The device consists of the following: A computer monitor (old CRT), a camera to observe the eye, an infrared (IR) lighting source, a chin rest (from an old ophthalmic slit lamp), a screen to block one of the eyes, and an adjustable table (from an ophthalmic retailer). This IR source is a series of readily available low intensity IR LEDs that are mounted together and powered in unison. A commercially available ground glass diffuser sits in front of the LEDs to spread the light. There is no opportunity for pain, discomfort, or damage to the eyes in any way. The device is investigational and will not be used to make a clinical diagnosis. It is one of a kind and not currently meant for distribution. There is no more than minimal risk to subject. B) The device will be labeling in accordance with 812.5, stating: "CAUTION--Investigational device. Limited by Federal (or United States) law to investigational use." C) Informed consent will state clearly that this is an investigational device only. D) Investigators will comply with the requirements of 812.46 with respect to monitoring investigations and notify the IRB immediately of any unexpected finding or realization that the device may represent more than minimal risk. E) The study coordinator will maintains the records required under 812.140(b) (4) and (5) - The name and intended use of the device and the objectives of the investigation; - A brief explanation of why the device is not a significant risk device: - The name and address of each investigator: - The name and address of each IRB

that has reviewed the investigation: - A statement of the extent to which the good manufacturing practice regulation in part 820 will be followed in manufacturing the device; and - Any other information required by FDA. - Records concerning adverse device effects (whether anticipated or unanticipated) and complaints and will make the reports required under 812.150(b) (1) through (3) and (5) through (10); F) The study coordinator and investigators will ensure that participating investigators maintain the records required by 812.140(a)(3)(i) and make the reports required under 812.150(a) (1), (2), (5), and (7);

Control, storage, and use of the device

How does the PI plan to store, control, and use the device?

Storage, control and use under supervision of the Principal Investigator

Section Q: Consent Form(s)

Study 1A and 1B

Study 2

Section R: Advertisements

None

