The optokinetic reflex (OKR) requires both visual function and cortical function. When presented with a drifting image of sinusoidally modulated gratings, the eye will reflexively track the stimulus (slow phase). At a certain point, the eyes will rapidly re-fixate in the opposite direction (fast phase) and then begin to track again. By adjusting the characteristics of the drifting image, contrast sensitivity thresholds can be measured. Others have attempted to use the OKR under photopic conditions to assess contrast sensitivity thresholds differences between normal patients and patients with glaucoma. These data suggest that it is possible to use contrast sensitivity to distinguish between these groups, but the investigators were restricted by the technologies available at the time and the cumbersome techniques used to track and record OKR-induced eye movements. Our new device takes advantage of a high resolution monitor, real time infrared light eye tracking, and intelligent software that adjusts the monitor-presented sinusoidally modulated gratings in response to patient eye movements to rapidly determine contrast sensitivity levels in 3-5 minutes per eye.

Section D: Purpose and Objectives

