Study 1: 20 adult subjects with no history of ocular disease and 20 adults subjects with definite glaucoma will be recruited to assist with optimization of device parameters. Study 1A: The individuals will not be patients of the co-investigators but rather volunteers who are recruited by word of mouth (co-employees, residents, research staff, etc.) and are willing to volunteer their time to assist in the development of the project. No coercion or implied benefits will be applied to recruit participants (see section E2). Volunteers can be of any age >18, male or female, and must be of self-reported excellent ocular health. Best spectacle corrected visual acuity of 20/40 or better is required (verified by Snellen acuity testing on the day of participation) and the participant must have no reported history of glaucoma, retinal disease, amblyopia, ocular trauma, or ocular surgery of any kind with the exception of refractive surgery (LASIK, PRK, or equivalent). Study 1B: These individuals will be recruited from the Alkek Eye Center patient population with confirmed diagnosis of glaucoma and of any age > 18.

Study 2: Potential subjects will be recruited from the Alkek Eye Center of the Department of Ophthalmology at Baylor College of Medicine and their families we will recruit 100 patients for this study in the following distribution:

- 1) 20 normal controls age 50 or older
- 2) 20 patients age 50 or older with ocular hypertension
- 3) 20 patients age 50 or older who are glaucoma suspects
- 4) 20 patients age 50 or older with early to moderate glaucoma
- 5) 20 patients age 50 or older with moderate to advanced glaucoma

Inclusion Criteria:

Normals for Study 1

1. Male or Female
2. age 18 or older
3. Corrected visual acuity 20/40 or better in both eyes.

Normal Controls for Study 2

1. Male or Female
2. age 50 or older

3. IOP 21 or less in both eyes
4. Corrected visual acuity 20/40 or better in both eyes.

Subjects with ocular hypertension

1. Male or Female
2. Age 50 or older
3. Defined as IOP > 21 without medication on two or more clinic visits in one or both eyes
4. Corrected visual acuity 20/40 or better
5. Normal optic nerves
6. Normal automated perimetry in both eyes

Subjects who are glaucoma suspects

1. Male or Female
2. Age 50 or over
3. Increased optic nerve cupping in one or both eyes regardless of IOP
4. Corrected visual acuity 20/40 or better
5. Normal automated perimetry in both eyes

Subjects with early to moderate glaucoma

1. Male or female

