2. Age 50 or over
3. Increased optic nerve cupping regardless of IOP in one or both eyes
4. Corrected visual acuity 20/40 or better in both eyes
5. Early to moderate perimetric changes defined as a mean deviation (MD) no less than -7.5 and a pattern standard deviation (PSD) no greater than +7.5 in the worse eye.

Subjects with moderate to advanced glaucoma

1. Male of Female
2. Age 50 or older
3. Increased optic nerve cupping regardless of IOP in one or both eyes
4. Grossly abnormal automated perimetry (MD less than -7.5 or PSD greater than +7.5 in the worse eye)
5. Best-corrected visual acuity of 20/40 or better in both eyes

Exclusion Criteria:

Normal Controls:

1. glaucoma or glaucoma suspicion in either eye
2. IOP > 21 in either eye
3. History of use of IOP-reducing drops in either eye except temporarily following cataract extraction
4. History of any ocular surgery except cataract extraction or refractive surgery (LASIK, ORK, or equivalent) in either eye
5. Retinal disease in either eye
6. Abnormal measured automated perimetry in either eye

7. Abnormal measured contrast sensitivity in either eye

F2. Procedure

The protocol is divided into two studies that will have two separate consent forms (Study 1A and B, and Study 2).

All participants requiring spectacle correction will use their own glasses or contact lenses or a pair of provided trial glasses (if needed) during the research study.

Study 1: Subjects participating in this portion of the study will attend one single visit:

1) Informed consent will be obtained and inclusion/exclusion criteria will be confirmed. Demographic information, ocular history, refraction, and visual acuity information will be collected for all patients. Additional clinical data will also be collected for Study 1B participants only. Information to be collected will include name, date of birth, ethnicity, gender, ocular history (surgery, etc), type of glaucoma (study 1B), current visual acuity, refraction, central corneal thickness (study 1B), intraocular pressure (study 1B), recent slit lamp exam including lens status (study 1B), recent dilated exam including optic nerve appearance (study 1B), and recent automated perimetry results (Humphrey visual field, study 1B)

2) Snellen visual acuity will be measured while wearing current spectacle correction to ensure acuity of 20/40 or better. The current spectacle correction (refraction) and acuity will be recorded.

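### The optokinetic threshold depends on eye movements and cortical function, but Study 1B and the Study 2 patient groups exclude no non-glaucoma cause of poor tracking, and the Study 2 controls drop the amblyopia and trauma exclusions of Study 1A

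*Combined protocol and SAP*

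**What the plan says.** **How the outcome is obtained.** Section C states: "The optokinetic reflex (OKR) requires both visual function and cortical function". It describes the device as using "intelligent software that adjusts the monitor-presented sinusoidally modulated gratings in response to patient eye movements to rapidly determine contrast sensitivity levels". The recorded eye movement is thus the only evidence that a grating was seen.

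**Eligibility (section F1).**
- *Study 1A volunteers:* each "must be of self-reported excellent ocular health", and "the participant must have no reported history of glaucoma, retinal disease, amblyopia, ocular trauma, or ocular surgery of any kind", with an exception for refractive surgery.
- *Study 1B:* "These individuals will be recruited from the Alkek Eye Center patient population with confirmed diagnosis of glaucoma and of any age > 18". No exclusions are listed. The Study 1 procedure in F2 adds a 20/40 acuity check.
- *Study 2 Normal Controls:* this group has the only exclusion list in the protocol. It starts with "glaucoma or glaucoma suspicion in either eye" and goes on to raised IOP, IOP-lowering drops, most ocular surgery, retinal disease, abnormal perimetry (item 6) and abnormal contrast sensitivity (item 7, test not named). Amblyopia and trauma are not on it.
- *Study 2 ocular hypertension and glaucoma suspects:* "Normal automated perimetry in both eyes", plus acuity of 20/40 or better. No exclusion list.
- *Study 2 glaucoma groups:* acuity of 20/40 or better in both eyes. No exclusion list.

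**Failed tests.** Sections G1 and J2 allow Study 1 participants to be retested after technical problems. Nothing says how an eye that does not track is scored.

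**The concern.** A person can fail to follow a drifting grating without any loss of retinal ganglion cell function. Nystagmus, manifest strabismus, another eye-movement disorder, or a stroke affecting vision or gaze can all do this. Amblyopia or old trauma can lower contrast sensitivity in one eye for reasons unrelated to glaucoma. The investigators thought amblyopia and trauma important enough to exclude in Study 1A. No reason is given for dropping them in Study 2, which supplies the age-relevant controls and all the graded disease groups.

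Two results are exposed. The first is the comparison between groups: if controls are filtered on contrast sensitivity and patients are not, non-glaucoma deficits are left on one side of the comparison. The second is the set of between-eye comparisons that G2 lists as primary. Numbers 1, 2 and 4 (scotopic, photopic, and scotopic-to-photopic ratio) can each show an asymmetry in a participant with one amblyopic eye and no glaucoma.

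**Working it through.** **Step 1. Which group is protected against what (F1 and F2).**

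| Group | Amblyopia or trauma named | Eye-movement or neurological disorder named | Partial protection |
|---|---|---|---|
| 1A | Yes | No | Self-reported excellent ocular health; acuity 20/40 |
| 1B | No | No | Acuity 20/40 (F2 check) |
| Study 2 controls | No | No | Acuity 20/40 in both eyes; abnormal perimetry and abnormal contrast excluded |
| Ocular hypertension, suspects | No | No | Acuity 20/40 (line does not say both eyes); normal perimetry in both eyes |
| Two glaucoma groups | No | No | Acuity 20/40 in both eyes |

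Protection is weakest in Study 1B and the two Study 2 glaucoma groups. In the latter, a field defect from a stroke could also contribute to the MD or PSD value that assigns a patient to a severity group.

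**Step 2. The plan's own figure.** Total N = 20 (1A) + 20 (1B) + 5 × 20 (Study 2) = 140, as stated in G1. There is no power calculation to reproduce; G2 says a sample size estimate is not possible.

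**Step 3. How many cases might enter.** The documents give no prevalence. Assume that a proportion p of participants has a relevant condition, with p between 2% and 5%.
- Chance of at least one case in a group of 20: 1 − (1 − p)^20. At 2%, 1 − 0.98^20 = 0.33. At 5%, 1 − 0.95^20 = 0.64.
- Expected cases per group of 20: 20p = 0.4 to 1.
- Expected cases in the 80 Study 2 patients: 80p = 1.6 to 4.

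**Step 4. What a case does to a group mean.** Assume that an affected participant scores c SD below the group mean. With k such participants in 20, the mean falls by kc/20.
- k = 1, c = 3: 3/20 = 0.15 SD.
- k = 2, c = 3: 6/20 = 0.30 SD.
- k = 3, c = 3: 9/20 = 0.45 SD.

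**Step 5. What it does to a test.** Simulated two-sided 5% t-tests, 20 per group, no true glaucoma effect, k patients set at 3 SD below the mean:

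| k | Rejection rate |
|---|---|
| 0 | about 5% |
| 1 | about 5% |
| 2 | about 9% |
| 3 | about 15% |

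A single case leaves the rate unchanged because the outlier also inflates the SD. If the number of cases is drawn at random, the rate is about 5.3% at p = 2% and about 6.6% at p = 5%.

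**Step 6. Scale.** With 20 per group, the difference detectable with 80% power is (1.96 + 0.84) × √(2/20) ≈ 0.89 SD. A shift of 0.15 SD is about one sixth of that.

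**The case against.** The strongest case on the other side has four parts.

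1. **Existing criteria already remove some of these people.** The acuity limit removes denser amblyopia. Normal perimetry removes stroke with field loss from the ocular hypertension and suspect groups. Control exclusions 6 and 7 take out controls with abnormal fields or contrast. The Study 1A health condition plausibly covers nystagmus and motility disorder. This stands, and it narrows the gap to Study 1B, the glaucoma groups, and disorders that spare acuity and fields. It also means that one cannot say affected controls simply widen the normal range, since some would be removed. The protection is uneven, however. If item 7 refers to Pelli-Robson, which F2 describes as a stationary test, it need not detect a tracking deficit. If it refers to the device, controls are selected on the outcome and patients are not.

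2. **A reader might infer that failures to track are counted as contrast loss.** The documents do not say so. With no scoring rule, such an eye could be given a floor value, treated as missing or repeated. What is documented is the absence of a rule. Likewise, section C says cortical function is required; it does not say that it must be intact.

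3. **The numerical effect is small.** This stands. The prevalence and the 3 SD deficit are assumptions, and having a condition is not the same as failing to track. An amblyopic eye that corrects to 20/40 may track adequately.

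4. **This is a pilot, and recording the conditions could serve instead of excluding them.** That is a fair alternative, but the baseline lists in F2 contain ocular history only, with no medical or neurological history. The information would not be there unless the plan asked for it.

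**Conclusion.** The point holds as an eligibility gap, concentrated in Study 1B and the Study 2 patient groups, with a smaller gap in the Study 2 controls for amblyopia and trauma. Where it acts, the likely direction is toward a glaucoma effect, because only the controls are screened on contrast.

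The size cannot be established from the documents. On the assumed 2% to 5% prevalence and 3 SD deficit it is modest: one case shifts a group mean by 0.15 SD with almost no change in false-positive rate, and it becomes material only if two or three cases fall in one group. The documents do not support a claim that the group comparisons are invalid. The change is worth making because it is cheap and because the plan already applies part of it in Study 1A.

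**What to change.** - **Eligibility.** Apply the Study 1A amblyopia and ocular trauma exclusions to Study 1B and to all five Study 2 groups. Add nystagmus, manifest strabismus or other eye-movement disorder, and stroke or neurological disease affecting vision or eye movements.
- **Ascertainment.** Use the ocular history already collected, plus one added medical and neurological history question.
- **Scoring rule.** State that an eye without a valid tracking response is flagged and analysed separately, and is not scored as low contrast. Add a sensitivity analysis that includes such eyes at the floor value.

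**Cost.** Protocol wording and one history item. A few patients become ineligible, and the results do not extend to them.

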In some cases, medical or graduate students may be asked to participate or request to participate. All participation will be completely voluntary and there will be no penalties for not participating. There will be no coercion at any point and there will be no benefit, real or implied, in participation.

E3. Pregnant woman/fetus

Will pregnant women and/or fetuses (as described in 45 CFR 46 Subpart B) be enrolled in the research?

No

E4. Neonates

Will neonates of uncertain viability or nonviable neonates (as described in 45 CFR 46 Subpart B) be enrolled in the research?

No

E5. Children

Will children be enrolled in the research?

No

Section F: Design/Procedure

F1. Design

Select one category that most adequately describes your research:

i) Device, Phase I, Single Center

Discuss the research design including but not limited to such issues as: probability of group assignment, potential for subject to be randomized to placebo group, use of control subjects, etc.

This protocol is divided into 2 studies. Study 1 involves the optimization of the device parameters. Study 1 will test adult subjects with no history of ocular disease (Study 1A) to assess the limits of human contrast sensitivity and subjects with definite glaucoma (Study 1B) by gathering preliminary data for comparison. These two pilot sub-studies intend to provide rapid data in regard to the device testing results to support the study hypothesis. This strategy will help rule out false negatives and false positives so that any adjustments can be made prior to the start of Study 2 for longitudinal data collection. Study 2 involves determination of baseline population parameters for an older population more likely to be age-matched with patients with glaucoma, as well as performance of patients with various levels of glaucoma severity.

Enrollment of participants in Study 1B will begin after the first 5 participants have been enrolled and tested in Study 1A. Study 2 will begin after Study 1A and B are complete.

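### Retinal disease is excluded in normals but in no patient group, and normal controls are also screened on contrast sensitivity, so normal v patient differences in contrast level can overstate the glaucoma effect

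*Combined protocol and SAP*

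**What the plan says.** **Normals.** F1 requires Study 1A volunteers to have "no reported history of glaucoma, retinal disease", among other conditions, by their own report. The only exclusion list in the protocol is headed for normal controls. Item 5 is "Retinal disease in either eye" and item 7 is "Abnormal measured contrast sensitivity in either eye". I read the list as the Study 2 list: its heading matches the Study 2 inclusion label, and it includes a perimetry item although Study 1A has no perimetry. Item 7 gives no test, cut-off or timing.

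**Patients.** Study 1B participants are "recruited from the Alkek Eye Center patient population with confirmed diagnosis of glaucoma and of any age > 18". Neither this description nor the inclusion list of any Study 2 patient group mentions retinal disease.

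**Partial safeguards.** Acuity of 20/40 or better applies throughout; for Study 1B it comes from the visit procedure in F2: "Snellen visual acuity will be measured while wearing current spectacle correction to ensure acuity of 20/40 or better". Ocular hypertension and glaucoma suspects need "Normal automated perimetry in both eyes". The early to moderate group has a cap: "Early to moderate perimetric changes defined as a mean deviation (MD) no less than -7.5", with a matching limit on pattern standard deviation.

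**Use of the comparison.** Study 1 tests "subjects with definite glaucoma (Study 1B) by gathering preliminary data for comparison", and G1 treats it as a baseline for the disease groups. Section C sets the aim of comparing contrast levels in normals with those in patients. G2 compares its measures among all patients and groups, and regards the normative database as critical for designing larger studies. G2 mentions multivariate analyses but names no covariate, and it gives no rule for participants with retinal disease.

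**The concern.** Section P gives the device's use as measuring contrast sensitivity. Section I expects it to help in monitoring retinal disease, although that is not assessed here. On the protocol's own account, then, retinal disease should affect the reading. A cause of low contrast that is barred on one side of a comparison and allowed on the other is confounded with glaucoma.

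Item 7 works on the other side. It removes the low end of the normal group on the construct that is being compared.

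At stake are the size of the normal v patient difference and the normal range. The protocol intends the Study 1 results to guide Study 2 and the normative data to guide larger studies. An inflated difference would make later studies too small, and a trimmed normal range would label too many healthy people abnormal.

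**Working it through.** **1. Which groups are exposed**

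| Group | Retinal disease barred? | Other limits on contrast loss |
|---|---|---|
| Study 1A normals | Yes, reported history | Acuity |
| Study 2 normal controls | Yes, either eye | Acuity, normal perimetry, item 7 |
| Study 1B glaucoma | No | Acuity |
| Ocular hypertension | No | Acuity, normal perimetry |
| Glaucoma suspects | No | Acuity, normal perimetry |
| Early to moderate | No | Acuity, MD/PSD cap |
| Moderate to advanced | No | Acuity |

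In the moderate to advanced group the perimetry criterion is a minimum severity, not a cap. F2 describes perimetry as a test of retinal function and sensitivity, so retinal loss from another cause could help an eye to qualify.

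**2. Inputs.** Group size is 20, from F1 and G1 (total 20 + 20 + 5 x 20 = 140, as stated). The documents give no prevalence of retinal disease, no loss, no SD, no alpha and no effect size. All values below other than group size are assumptions, in units of the device's SD.

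**3. Retinal disease.** Bias in the mean difference = prevalence x loss.
- Low: 0.05 x 0.5 = 0.025 SD.
- Middle: 0.20 x 1.0 = 0.20 SD.
- High: 0.30 x 2.0 = 0.60 SD.

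With an assumed true effect of 0.5 SD, the apparent difference runs from 0.5 + 0.025 = 0.525 SD (1.05 times the truth) to 0.5 + 0.6 = 1.1 SD (2.2 times).

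**4. Item 7.** Let q be the share of normals below the cut-off in one eye (2.5-5%) and rho the correlation of the screening test with the device (0.5-1.0). For screening on one eye, the shift in the normal mean = rho x phi(z_q)/(1 - q).
- q = 2.5%, rho = 0.5: 0.5 x 0.060 = 0.03 SD.
- q = 5%, rho = 1: 0.11 SD.

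The criterion is either eye, which removes more people. A bivariate normal simulation with between-eye correlation 0.5-0.9 gives shifts of about 0.04 SD (q = 2.5%, rho = 0.5) to 0.14 SD (q = 5%, rho = 1). A lower limit set at the 2.5th percentile of the screened normals then flags about 3.0-8.2% of unscreened normals instead of 2.5%.

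This shift applies to Study 2 only. It adds to the retinal bias there, because the two act on different means.

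**5. Precision of a sensitivity analysis.** 95% CI half-width = t x sqrt(1/20 + 1/n), where n patients remain against 20 normals.
- n = 20: 0.640 SD
- n = 18: 0.659 SD
- n = 16: 0.682 SD
- n = 14: 0.710 SD

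This counts patients. A patient who loses only one eye may still contribute the other.

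**The case against.** **Healthy controls are ordinary practice, and this is a pilot of a device that will not be used for diagnosis.** Both are true. Excluding retinal disease in normals is reasonable. The fault is doing so on one side only, with no analysis to separate the causes. The pilot status limits the harm, but the protocol gives these data a role in later design.

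**The patient groups have safeguards.** This stands in part. Normal perimetry and the MD/PSD cap make the low end of the range more fitting for three of the four Study 2 patient groups. It does not help Study 1B or the moderate to advanced group. Section C itself says that contrast can fall while acuity is preserved, so a 20/40 limit is weak protection.

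**A reader might infer that every primary comparison is biased in the device's favour.** The documents do not support that. G2 lists between-eye comparisons, scotopic v photopic contrast within an eye, and relations to perimetry and Pelli-Robson. Similar loss in both eyes would largely cancel in a between-eye difference, and nothing fixes the direction for a scotopic/photopic ratio. The argument holds for contrast level. Comparisons among patient groups do not face the one-sided exclusion.

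**A reader might infer a high false-positive rate.** With no glaucoma effect, 30% prevalence and a 2 SD loss, a two-sided 5% t-test at 20 v 20 rejects about 33% of the time. That pairs extreme inputs with a zero effect in the groups where zero is least plausible. With 5-20% prevalence and a loss of 0.5-1 SD, the rate is about 5-9%. G2 also specifies no alpha or formal test.

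**A reader might infer that item 7 screens normals with the study device.** The text does not say so. The only contrast tests in the Study 2 schedule are the device and Pelli-Robson, the latter at the second research visit, but item 7 could refer to earlier clinic records. The smaller correlations in the working allow for that.

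**Conclusion.** The point holds for normal v patient comparisons of contrast level. Retinal disease is barred in both normal groups and in no patient group, and item 7 selects normal controls on the construct the device measures. Both raise the apparent difference, if retinal disease lowers the reading as Section I implies. Exposure is greatest in Study 1B and the moderate to advanced group.

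The size cannot be found from the documents. The retinal bias of 0.025-0.6 SD and the item 7 shift of about 0.04-0.14 SD rest wholly on the assumed inputs; only the direction follows from the eligibility rules. Since the protocol expects glaucoma to lower contrast, the likelier harm is an exaggerated effect. For item 7 the effect on the mean is small, and the effect on the normal range matters more. The plan should be changed, as the remedies are cheap.

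**What to change.** 1. **Study 2.** Apply the retinal-disease exclusion to all five groups, using the ocular history and dilated examination already collected at baseline. Or keep broad patient groups and prespecify in G2 a sensitivity analysis of the normal v patient comparisons without eyes that have non-glaucomatous retinal disease.
2. **Study 1.** Use the same reported-history criterion in 1A and 1B, or run the same sensitivity analysis. An examination-based exclusion in 1B alone would not match, because 1A has no dilated examination.
3. **Item 7.** Drop it, so that normals are defined without reference to contrast sensitivity.

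**Cost.** A common exclusion slightly slows recruitment and narrows the patient population. The sensitivity analysis loses no recruits; if 14-18 of 20 patients remain, its 95% CI half-width is 0.66-0.71 SD instead of 0.64 SD. Dropping item 7 makes the normal range slightly wider and the group difference slightly less favourable. These options need no new test or visit. Keeping item 7 in a defined form would not be as cheap: it would need an earlier contrast test, or extra normals to replace those excluded.
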